Secondary Aim: To compare the effect of electronic cigarettes with nicotine to electronic cigarettes without nicotine on smoking behavior (combustible cigarettes) among African American menthol and non-menthol smokers.

Secondary Hypothesis: At 6 weeks post-enrollment, there will be a greater reduction in use of combustible cigarettes among participants using electronic cigarettes with nicotine compared to participants using electronic cigarettes without nicotine.

Significance

Approximately 1 in 4 adult smokers in the U.S. smoke mentholated cigarettes.¹ However, there is substantial variation in the use of mentholated cigarettes.¹ Up to 80% of African American smokers use mentholated cigarettes compared to approximately 25% of non-Hispanic white smokers.² African

Americans also experience disproportionately high rates of lung cancer² and other smoking-related diseases.^{3, 4} Studies by our research team⁵⁻⁷ and others⁸ have suggested that mentholated cigarettes are more addictive and associated with lower quit rates compared to non-mentholated cigarettes. However, not all studies have found this association.^{9, 10} The pattern of use of mentholated cigarettes in Minnesota is consistent with national data in that 22% of smokers used mentholated cigarettes in 2010 and the rates of menthol use is highest among priority populations including African Americans, unemployed, and low-income smokers.

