Unfortunately, clinical studies assessing the efficacy of e-cigarette for smoking cessation per se cannot begin without an Investigational New Drug (IND) for a chosen e-cigarette from the FDA;¹³ IND approval requires a level of product data and manufacturing documentation that is currently not available to researchers. Efforts by our research team as well as other researchers to obtain an IND approval from the FDA have been unsuccessful. In view of the barrier created by the current FDA policy requiring IND approval for e-cigarettes, it has therefore become necessary to amend the design of the proposed study from a treatment study to one that will assess the patterns of use of e-cigarettes and changes in biomarkers of exposure among African American smokers.

Because the primary outcome of the amended design is changes in biomarkers among smokers not intending to quit rather than smoking cessation, it is our belief that IND is not required. Under current FDA regulatory environment, the amended design represents the best possible science that uses a randomized controlled design to fill critical gap in the tobacco control literature regarding the patterns of use of e-cigarettes among African American smokers. The proposed study is informed by findings from our formative research which demonstrated an overwhelming preference for menthol e-cigarettes by African American menthol smokers and therefore represents an important step for developing an evidence base for about e-cigarette use in this priority population and its impact on potential harm.

Preliminary Evidence

Our research team recently completed a ClearWay-funded pilot study (n=53) to determine cessation treatment preferences of menthol cigarette smokers in which menthol smokers tested six products including four types of nicotine gum (2mg & 4mg plain; 2mg & 4mg mint-flavored) and two flavors of electronic cigarettes (16mg menthol and non-menthol). Study enrollment was completed in about six weeks. Participants were all African American menthol smokers, 53% male, mean age 45.5 (SD=11.5) years, smoked 14.2 CPD at baseline (SD=5.1).

Of the 53 smokers who completed product selection phase, 73.5% selected menthol e-cigarettes, 18.9% selected non-menthol e-cigarettes, and 7.5 % selected 2mg mint nicotine gum for smoking cessation. At the final week six follow-up visit (after two weeks of using selected product),

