participants on average smoked 4.5 CPD; they reported using 8.7 e-cigarettes total for the 2-week cessation phase (<1 e-cig/day); and four participants had quit smoking tobacco cigarettes.

Findings from our formative research informed the proposed study in a number of ways including, 1) the formative research showed that African American menthol smokers will engage in a clinical research that includes the use of e-cigarettes. Given that recruitment of the 50 participants was completed in less than two months with minimal attrition, established the feasibility of recruitment for the proposed study; 2) African American menthol smokers overwhelmingly preferred menthol e-cigarettes compared to other tested products as a smoking cessation aid. This finding informed our choice of menthol e-cigarettes for the proposed study; and 3) given the absence of data on the patterns of use of e-cigarettes and the impact of use on biomarker of exposure, a natural step is for a study to evaluate the effects of e-cigarette on smoking behavior in this population

Innovation

The proposed study is innovative in that it will be the first to determine the biomarkers associated with the use of e-cigarettes among African American menthol and nonmenthol smokers, and to determine the pattern e-cigarette use among this priority population. In addition, this study will examine the role of nicotine in pattern of e-cigarette use and biomarkers of exposure.

Both nationally and in Minnesota, racial/ethnic minorities as well as other at risk groups (e.g. youth, low SES) smoke menthol cigarettes at disproportionately high rates compared to the general population. These groups also experience disproportionately higher rates of tobacco-related socio-economic and health consequences compared to the general population. The proposed research will examine patterns of use of e-cigarettes among smokers of combustible cigarettes in this priority population of smokers and the impact of these behaviors on biomarkers of exposure. Such information is critical to addressing use of tobacco products among at-risk smokers in Minnesota and nationally.

Approach

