- 1) Overall design: The current study design was informed by findings from our formative study that showed that African American menthol smokers overwhelmingly selected menthol e-cigarette for smoking cessation. Using a randomized design would reduce potential differences in smoking behavior (e.g. CPD, motivation and confidence to quit, quit attempts, psychosocial factors, etc) between study groups that might impact the outcomes of interest. A 2-group randomized design will be used to evaluate the patterns of use of e-cigarette and the impact of use on biomarkers of exposure.
- 2) How was the brand and dose of e-cigarette selected? In our recently completed pilot study, we used the Blu e-cigarette (approximately 13-16mg nicotine) which is among the most commonly used and widely available e-cigarettes. The product was well-liked and well-tolerated by participants. However, there are more recent generations of e-cigarettes that may deliver a higher amount of nicotine. Therefore, if this proposal is funded, we will review all available options in the market and consider factors such amount of nicotine delivered, price, and affiliation of manufacturer with tobacco industry in final product selection with guidance from [name], an e-cigarette expert on our team.
- 3) Why limit study sample to African Americans? There are well-documented differences in smoking patterns and nicotine metabolism between African Americans (AAs) and whites. These include the fact that AAs smoke fewer cigarettes per day and predominantly smoke menthol cigarettes.²⁹ AAs also have higher cotinine levels per cigarette smoked than whites.³⁰ Differences in smoking patterns and nicotine metabolism in specific populations could introduce variability that masks potential differences in how smokers use e-cigarettes effects. Also, in the TPSAC report to the FDA, the population that had lower success rates for smoking cessation among menthol smokers compared to non-menthol smokers was predominantly African American (<http://www.fda.gov/downloads/AdvisoryCommittees/CommitteesMeetingMaterials/TobaccoProductsScientificAdvisoryCommittee/UCM269697.pdf>).

4

Table 2. Project Timeline

| | Year 1 | | | Year 2 | | | Year 3 | | |
|---------|--------|-----|------|--------|-------|-------|--------|-------|-------|
| Months: | 1-4 | 5-8 | 9-12 | 13-16 | 17-20 | 21-24 | 25-28 | 29-32 | 33-36 |

| | | | | | | | | | |
|--|--|--|--|--|--|--|--|--|--|

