Prior to initiating outcome analyses of quantitative data, we will examine frequency distributions for all variables, with particular attention to variable ranges, missing values, and skewness, and will log-transform variables as necessary. Using t-tests for continuous data and chi-square tests for categorical data, we will examine randomization group comparability at baseline to determine whether randomization was successful in creating equivalent groups with regard to the demographic variables and baseline characteristics (i.e. age, gender, cigarettes smoked per day, nicotine dependence, and menthol vs. regular cigarette smoker). These analyses, along with a priori reasoning will help determine whether there is a need to incorporate covariates into later analyses.

Primary analyses: The primary outcome for the study will be NNAL at week 6. We will compare week 6 NNAL between the two study groups, adjusted for baseline NNAL in generalized linear regression models. Covariates that will be considered include age, sex, income or educational level, and menthol status. To test for a within-subject change in NNAL from baseline to week 6, paired t-tests will be used within randomization group.

Secondary analyses: Differences in our secondary measures between the two study groups will be assessed using the appropriate methods (e.g., logistic regression for binary and binomial outcomes, linear regression for continuous outcomes; using their Generalized Estimating Equations or mixed model analogs when the outcomes were repeatedly measured within person). Specifically, differences in smoking behavior between the two groups will be assessed by comparing the change in average number of cigarettes per day on the 7 days preceding the baseline visit to each study time point (week 2, week 6, and week 12). Other secondary measures that will be compared between the two groups may include: change in TNE from baseline to follow up visits, e-cigarette use from baseline to week 6, e-cigarette use from week 6 to week 12, and e-cigarette product evaluation.

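### Cigarettes per day is compared as change from baseline with no commitment to adjust for baseline, which gives up precision on the secondary hypothesis

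*Combined protocol and SAP*

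**What the plan says.** The secondary hypothesis in Specific Aims is: "At 6 weeks post-enrollment, there will be a greater reduction in use of combustible cigarettes among participants using electronic cigarettes with nicotine", compared with the nicotine-free arm. The Analysis Plan, under Secondary analyses, tests it as follows: "differences in smoking behavior between the two groups will be assessed by comparing the change in average number of cigarettes per day", using a 7-day average at baseline and at weeks 2, 6 and 12. The model family is linear regression, or its GEE or mixed-model counterpart for repeated outcomes. No covariate is named for CPD.

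The primary outcome is handled differently: "We will compare week 6 NNAL between the two study groups, adjusted for baseline NNAL in generalized linear regression models". The covariates to be considered there are age, sex, income or education, and menthol status; baseline CPD is not among them.

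Baseline CPD is one of the variables tested for comparability between arms, and the plan adds: "These analyses, along with a priori reasoning will help determine whether there is a need to incorporate covariates into later analyses". Change in TNE is an optional further comparison, also with no baseline term stated: "Other secondary measures that will be compared between the two groups may include: change in TNE from baseline to follow up visits".

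**The concern.** Subtracting baseline is not the same as adjusting for it. A change score fixes the slope of follow-up on baseline at 1, whereas regression estimates it. When the true slope is not 1, the change score carries avoidable noise and moves with any chance baseline difference between the arms.

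The plan's covariate rule does not close the gap. A test of whether the arms differ at baseline says nothing about whether baseline CPD predicts follow-up CPD, and that prediction is what yields precision. The reference to a priori reasoning permits adjustment without committing to it, so the model for the only stated secondary hypothesis could be settled after data have been seen.

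At stake is the precision of that comparison. Its validity is not in question.

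**Working it through.** **The plan's own figure.** The Power Calculation covers NNAL only: 200 completers (100 per arm), difference 0.32, SD 0.80, two-sided alpha 0.05. The standardized difference is 0.32/0.80 = 0.4, and the noncentral t distribution gives 80.4% power, so the stated 80% reproduces. No power or sample size is stated for CPD.

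**Inputs for CPD**
- 100 completers per arm (Power Calculation, 1:1 allocation).
- Baseline SD 5.1 CPD (pilot study, Preliminary Evidence), used only to express results in CPD.
- Correlation ρ between baseline and follow-up CPD: not in the documents; assumed 0.3 to 0.9.
- k = follow-up SD / baseline SD: not in the documents; assumed 0.75 to 1.25. Pilot mean CPD fell from 14.2 to 4.5, but in a cessation phase and with no follow-up SD reported, so this does not fix k.

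**Formulas**, in units of the baseline variance, for one follow-up visit:
- Change score: 1 + k² − 2ρk
- Baseline-adjusted: k²(1 − ρ²)
- Difference: (1 − ρk)², which is never negative
- Proportional cut: (1 − ρk)² / (1 + k² − 2ρk), zero only when the slope ρk = 1

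**Equal SDs (k = 1).** The cut simplifies to (1 − ρ)/2. The 95% CI half-width is t × 5.1 × √(2/100) × √variance, where 5.1 × √(2/100) = 0.72 and t is about 1.97.

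| ρ | Variance, change | Variance, adjusted | Cut | Half-width, change | Half-width, adjusted | Completers needed if adjusted, 200 × (1 − cut) |
|---|---|---|---|---|---|---|
| 0.3 | 1.40 | 0.91 | 35% | 1.68 | 1.36 | 130 |
| 0.5 | 1.00 | 0.75 | 25% | 1.42 | 1.23 | 150 |
| 0.7 | 0.60 | 0.51 | 15% | 1.10 | 1.02 | 170 |
| 0.9 | 0.20 | 0.19 | 5% | 0.64 | 0.62 | 190 |

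In power terms (normal approximation), an effect that gives the change score 80% power gives the adjusted test 93.5%, 89.9%, 86.0% or 82.0% at these correlations.

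**Unequal SDs**

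| ρ | Cut, k = 0.75 | Cut, k = 1.25 |
|---|---|---|
| 0.3 | 54.0% | 21.6% |
| 0.5 | 48.1% | 10.7% |
| 0.7 | 44.0% | 1.9% |
| 0.9 | 49.7% | 5.0% |

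Within these ranges the smallest cut is 0% (for example at ρ = 0.8, k = 1.25, where ρk = 1) and the largest is 54.0%.

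**Cost of estimating the slope.** About 1/(2n − 4) = 1/196 = 0.5% of variance at n = 100 per arm.

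**Chance imbalance.** One standard error of the baseline difference is 0.72 CPD. With k = 1 it shifts the change contrast by (1 − ρ) × 0.72, which is 0.50, 0.36 or 0.22 CPD at ρ = 0.3, 0.5 or 0.7.

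**Simulation check.** With 20,000 simulated trials per setting, 100 per arm and no effect, the mean error of both estimators stayed within 0.0015 baseline SD. The simulated cuts were 34.6%, 25.0%, 14.7% and 4.8% at k = 1, close to the formula.

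**The case against.** The strongest reply is that nothing here is wrong. The comparison is unbiased, it matches a hypothesis worded as a reduction, the outcome is secondary and unpowered, and the size of the gain is unknown and could be zero. Variance percentages also flatter the case: at k = 1 the confidence interval narrows by only about 19%, 13%, 8% or 3%. The SD of 5.1 comes from 53 menthol smokers, whereas this trial also enrols nonmenthol smokers, and the plan may log-transform skewed variables, in which case the half-widths in CPD do not apply. All of this stands, and it limits the point to an avoidable loss of precision.

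A second reply is that the plan may adjust anyway, through a mixed model or through its covariate rule. A mixed model does not do so as written. One fitted to change scores contains no adjustment unless a term is added. One with baseline as a response and free arm-by-time means returns the change-score contrast when data are complete. Constraining the baseline means to be equal across arms would recover the precision, but the plan does not say so. The covariate rule only permits adjustment.

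It can also be said that Rationale for Study Design mentions CPD only to justify randomizing. That is a fair reading of its purpose. Still, the sentence refers to "smoking behavior (e.g. CPD, motivation and confidence to quit, quit attempts, psychosocial factors, etc) between study groups that might impact the outcomes" of interest, so the plan itself supplies the a priori reason to treat CPD as prognostic.

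Finally, a single baseline slope shared across weeks 2, 6 and 12 need not deliver the full week 6 gain, and baseline should not enter a model both as covariate and as response. Both points are correct and are covered in the fix.

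**Conclusion.** The concern holds. The plan compares change in CPD without committing to a baseline term, and no other section supplies one. The analysis as written is valid and no stated power or sample size is affected.

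The cost is precision on the only stated secondary hypothesis: 5% to 35% of the variance for correlations of 0.9 down to 0.3 with equal SDs, and 0% to 54% when the SD ratio varies from 0.75 to 1.25. These figures rest on assumed correlations and SD ratios and on a single-visit linear comparison. That the adjusted analysis is at least as precise in large samples does not depend on the assumed values; at worst it costs about 0.5% of variance here. The same reasoning applies to change in TNE if that is compared, though its size cannot be given from the documents.

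**What to change.** Add to Secondary analyses that baseline 7-day average CPD is a pre-specified covariate in the CPD model at weeks 2, 6 and 12, regardless of the comparability tests. The outcome may remain change: in a linear regression that includes baseline CPD, the arm estimate is the same for change and for the follow-up value. In a repeated-measures model, let the baseline slope differ by visit and do not also enter baseline as a response. If CPD is log-transformed, use the same scale for the baseline term. If change in TNE is analysed, adjust it for baseline TNE in the same way.

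The cost is wording only. Table 1 already schedules CPD, TNE and NNAL at the baseline visit, so no new data, visits or participants are needed.

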Protocol

Changes in Biomarkers Associated with Use of Electronic Cigarettes among African American Menthol and Nonmenthol Smokers

PI: [name], MPH

Version: 6

Date: 7/26/2019

CPRC#: 2015NTLS139

IRB#: 1509M78241

ClinicalTrials.gov#: NCT03084315

CTSI ID: 24127

Specific Aims

In this study, a 2-group randomized design will be used to evaluate changes in biomarkers associated with the use of e-cigarettes with and without nicotine among African American menthol and nonmenthol cigarette smokers. 240 smokers (all African American) will be randomized into one of two study groups including 1) Active e-cigarettes (containing nicotine), or 2) nicotine-free e-cigarette (containing 0mg nicotine). Within each study condition, participants will be allowed to select their preferred flavor (menthol or non-menthol) of electronic cigarettes after sampling both flavors.) Blocked randomization will be performed to ensure balance in the number of intervention assignments between the study groups (i.e., active e-cigarette versus nicotine-free e-cigarette). The power calculation for this study is based a two-sided two-sample equal-variance t-test on the primary outcome of NNAL (pmol/mg creatinine) at week 6 (active e-cig group vs. control e-cig group), and assumes an alpha of 0.05, and an NNAL standard deviation of 0.80. With a sample size of 200 completers, this study will have 80% power to detect a difference in NNAL between the active and placebo e-cig groups of at least 0.4 standard deviations at week 6 (mean difference of 0.32 pmol/mg creatinine).

All participants will be provided with e-cigarettes for *ad lib* use based upon the study randomization assignment. Follow-up assessments will be conducted at 2, 6, and 12 weeks post randomization. Primary outcomes will be changes in biomarkers, including total nicotine exposure (TNE) and 4-(methylnitrosamino)-1-(3-pyridyl)-1-butanol (NNAL). Secondary outcomes will be the patterns of use of combustible cigarettes and electronic cigarettes including dual use.

Primary Aim: To compare the effect of electronic cigarettes with nicotine to electronic cigarettes without nicotine on NNAL (a biomarker related to the use of combustible cigarettes) among African American menthol and non-menthol smokers.

Primary Hypothesis: At 6 weeks post-enrollment, there will be a greater reduction in NNAL among participants using electronic cigarettes with nicotine compared to participants using electronic cigarettes without nicotine.

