A total of 240 (all African American smokers) will be randomized 1:1 into one of two groups: nicotine-containing electronic cigarettes or nicotine-free electronic cigarettes. All participants will be provided with e-cigarettes by the study, based upon the study randomization assignment and be asked to use ad lib. Follow-up assessments will be conducted at 2, 6, and 12 weeks post randomization. Primary outcomes will be assessment of urinary biochemical markers NNAL (tobacco-specific carcinogen) and total nicotine exposure (not specific to tobacco) (TNE). Secondary outcomes will be the patterns of use of combustible cigarettes and e-cigarettes.

Inclusion criteria: 1) self-identify as African American or Black; 2) age 18 years or older; 3) smoke at least five cigarettes daily for the past year; 4) Willing to use e-cigarettes; 5) Good physical

health (no unstable medical or mental health condition); 6) no contraindications for e-cigarette use; and 7) does not have a set quit-date in the next 30 days.

Exclusion criteria: 1) Recent unstable or untreated psychiatric diagnosis including substance abuse, as determined by the DSM-IV criteria; 2) use in the past 30 days of e-cigarettes; 3) pregnant or nursing.

Recruitment: will utilize methods we have successfully used in previous studies with African American smokers³³⁻³⁶ including flyers at African American community, clinic, and university sites and events, paid advertisement in targeted newspapers, radio, and email panels with predominantly large African American audience. We will also post advertisements on Facebook and create a study Facebook page. Lastly, we will send recruitment letters to Fairview patients using the Fairview Research Recruitment Mailing service. In order to complete this process we will develop a mailing list through CTSI. Fairview will receive the mailing list and then work with UMN Addressing and Mailing to send our recruitment letter along with a Fairview cover letter to potential participants. Potential participants will then contact the study coordinator if they are interested in participating.

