Randomization Scheme: Randomization will occur at the individual level at the baseline assessment. The study statistician will provide the study coordinator with group assignments in sealed envelopes that will only be opened after study staff have confirmed eligibility and completed final consent. To ensure balance in the number of intervention assignments between the study groups (i.e., active e-cigarette versus nicotine-free e-cigarette), blocked randomization will be performed and the size and sequence of which will only be known to the statistician.

Study Procedures

Baseline/Randomization visit: At this visit the study's goal and procedures as well as participant responsibilities will be reviewed with each participant. Those who are interested will sign a consent form and be asked to complete an expired carbon monoxide assessment to verify smoking status. If expired carbon monoxide is <8ppm, then a urine sample will be collected and tested with urine strips for the presence of cotinine. If expired carbon monoxide is <8ppm and cotinine is not detected in the urine, the participant will be ineligible. Eligible participants will complete baseline assessments including demographics, tobacco use, and nicotine dependence measures. Participants will then be randomized to receive either active e-cigarettes (containing nicotine), or nicotine-free e-cigarette (containing 0mg nicotine). Within each study condition, participants will be allowed to select their preferred flavor (menthol or non-menthol) of electronic cigarettes. Prior to selection of their preferred flavor, participants will be allowed to sample both menthol and non-menthol flavored brands of e-cigarettes by taking a few puffs from both brands during the visit. Participants will receive enough supply of study products to last until their next appointment plus 7 days extra for scheduling flexibility. All participants will be provided verbal and written usage instructions for e-cigarettes. They will be instructed to bring all, used and unused, e-cigarettes to every visit for product count as one of the measures of adherence. Urine will also be collected to assess NNAL and TNE.

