Weeks 2 and 6: Approximately three days before each of these visits, participants will be contacted by study staff through reminder card and by phone. At these visits participants will update their contact information and complete a brief survey (combustible cigarettes and e-cigarettes use, withdrawal symptoms, etc), take expired CO test, and receive more e-cigarettes (week 2 only) to last until their week 6 visit. Study staff will check and record if participant has been actively using their e-cigarettes and count returned e-cigarettes. Urine will also be collected at week 6 to assess NNAL and TNE.

Week 12: Participants will complete a survey over the phone.

Compensation: Participants will be compensated for their time and transportation to minimize attrition. Based on our experiences in previous studies participants will receive \$40 at baseline and week 2, \$50 at week 6 visit, and \$20 at week 12, for a maximum of \$150 per participant over 12 weeks.

Nicotine E-Cigarette Arm: Participants will receive an active (brand and dose TBD) e-cigarette with the flavor of their choice. Participants will each be dispensed a free rechargeable e-cigarette starter kit with the necessary accessories at the randomization visit plus enough supplies at this visit and the week 2 visit for a total supply of 6 weeks. Trouble shooting support will be provided as well as phone numbers for both technical and medical assistance related to the use of e-cigarettes. Follow-up visit schedule and all other study protocol for participants in each arm will be the same. Although the study will only provide participants with e-cigarettes for 6 weeks, they will be told that they are allowed to purchase their own if needed after 6 weeks.

Nicotine-free E-cigarette arm: Participants will receive e-cigarettes containing 0mg nicotine with the same protocol described for the active e-cigarette arm above.

Human Subjects Protection:

This study will enroll 240 smokers, all African American. Inclusion and exclusion criteria have been discussed earlier in the proposal. Before any research is conducted, we will obtain IRB approval for the study protocol and informed consent documents. Data will be obtained exclusively for research purposes.

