Data Management: Data management activities for this project will encompass data entry, data cleaning, identifying and tagging any crossovers, conversion into proper format for data analysis and recoding. REDCap will be used for designing, implementation and maintenance of the database. In addition, a computer based tracking system will be developed to follow each patient and to prompt the staff for the upcoming data collection point. Data collection points for each subject will be calculated from his or her initial date of contact. Data entry will be performed at the University of Minnesota. Codebooks will be developed and will include variable formats (numeric/alpha), min/max ranges and any skip patterns.

References

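### Does an undefined starting date, with no stated window around week 6, leave the timing of the primary NNAL sample open?

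*Combined protocol and SAP*

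**What the plan says.** Four parts of the protocol bear on when the primary sample is taken.

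- **Time origin.** Data Management: "Data collection points for each subject will be calculated from his or her initial date of contact". Approach: "Follow-up assessments will be conducted at 2, 6, and 12 weeks post randomization"; Specific Aims says the same. The primary hypothesis in Specific Aims uses a third term: "At 6 weeks post-enrollment, there will be a greater reduction in NNAL". Randomization Scheme: "Randomization will occur at the individual level at the baseline assessment". Table 1 labels the Baseline/Randomization visit as Week 0 and as contact 1. An unnumbered screening column sits 7 to 14 days earlier.
- **The sample.** Study Procedures, Weeks 2 and 6: "Urine will also be collected at week 6 to assess NNAL and TNE". Analysis Plan, Primary analyses: "The primary outcome for the study will be NNAL at week 6". Neither section, nor Table 1, gives a plus-or-minus number of days.
- **Product supply.** Study Procedures, Baseline/Randomization visit: participants get "enough supply of study products to last until their next appointment plus 7 days extra for scheduling flexibility". The text for weeks 2 and 6 says that the week 2 dispensing is meant to carry the participant to the week 6 visit. The Nicotine E-Cigarette Arm paragraph says that what is handed out at the two visits adds up to six weeks.
- **After supply ends.** The same paragraph says of participants that "they will be told that they are allowed to purchase their own if needed after 6 weeks".

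**The concern.** The sentence in Data Management follows directly on the description of the tracking system that prompts staff for the next visit, so it looks like the working rule for scheduling. Contact does occur before randomization, because Table 1 collects cigarettes per day, demographics and smoking history at screening. If the clock started there, the week 6 urine would be taken after only four to five weeks on the assigned product.

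Even with the origin settled, the sample day is not bounded. The protocol expects visits to slip, since it hands out spare product for that purpose. A sample taken after day 42 might follow days without study product, or days on a self-bought device with or without nicotine. Either would weaken the contrast between arms. With no written rule, someone might also decide after seeing results whether a late sample counts as week 6.

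**Working it through.** **The plan's own figure.** Power Calculation gives 200 completers for 80% power, with SD 0.80, difference 0.32 (0.4 SD) and two-sided alpha 0.05. The normal approximation gives n per arm = 2 × (1.960 + 0.842)² / 0.4² ≈ 98.1, so 99. The exact t-test needs 100 per arm, with power 80.4%. The figure reproduces. It takes no input for visit timing.

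**Time origin.** Week 6 from randomization is 6 × 7 = day 42. There are two readings of the contact date:

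| Reading | Week 2 falls on | Week 6 falls on | Share of 42 days |
|---|---|---|---|
| Randomization (Week 0) | day 14 | day 42 | 100% |
| Screening, 7 days earlier | 14 − 7 = day 7 | 42 − 7 = day 35 | 83% |
| Screening, 14 days earlier | 14 − 14 = day 0 | 42 − 14 = day 28 | 67% |

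If screening were the origin, and if the arm difference scaled in proportion to days of exposure (an assumption with no support in the protocol), the difference would fall to 0.32 × 35/42 = 0.27 or 0.32 × 28/42 = 0.21. Power at 100 per arm would be 65% or 47%. That is why the phrase deserves a check.

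The screening reading fails that check. With a 14-day lead, the first follow-up visit would land on the day of randomization, before any product had been used. Approach and Specific Aims count from randomization. Table 1 has a row for visit or contact number, and its contact 1 is the Baseline/Randomization visit, while screening carries no number. The hypothesis counts from enrollment, but consent and randomization take place at the same baseline visit, so that origin is also day 0. Every origin the rest of the protocol supports gives a shift of 0 days.

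**Sample window.** The only tolerance the protocol mentions is the 7 spare days of product. A visit that late falls on 42 + 7 = day 49. Days beyond study supply by then:

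- Visit by visit: 14 + 7 at baseline, then 28 at week 2, makes 49 days. Days uncovered: 49 − 49 = 0.
- By the six-week total: 42 days. Days uncovered: 49 − 42 = 7, and 7/49 = 14%.

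The upper figure assumes that all product is used up on day 42. Use is ad lib, unused product is brought back to visits, and the week 2 dispensing is tied to the week 6 visit rather than to a calendar day, so 14% is a ceiling for a visit 7 days late. It is a share of days, not an effect on NNAL. The protocol gives neither the proportion of late visits nor a clearance rate for NNAL, so it cannot be turned into a loss of power.

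**What a written rule would change.** Table 1 and the visit text tie the urine to the week 6 visit, and Power Calculation counts those who complete that visit. The implied rule is that the sample from that visit is the week 6 sample. Writing down that all such samples enter the primary analysis gives the same data set and the same estimate.

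A sensitivity analysis limited to samples within 7 days of day 42 (days 35 to 49) would not test the worry. It keeps days 43 to 49, which are among the days in question. Its lower limit has no source in the protocol, and it treats a one-sided product allowance as a sampling tolerance. It also selects participants on something that happens after randomization.

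**The case for a change.** The best case for a change is that the primary outcome rests on one urine sample, the protocol itself foresees late visits, and day 42 is when free supply may stop and self-purchase is allowed. A control participant sampled late could be using a nicotine device. A line in the plan and one derived variable would cost almost nothing and would remove any discretion over late samples.

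Part of this stands. No window is given, the contact date is loosely worded, and the supply statements do not agree. A very late sample, some weeks beyond day 49, is not addressed at all.

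The rest is weaker. The self-purchase sentence most naturally covers the time between the end of supply and the week 12 phone survey, and nothing ties it to the week 6 urine. Reminders about three days before each visit and the tracking prompts limit drift. Both arms follow the same schedule, so lateness unrelated to arm would add noise or dilute the difference rather than bias it. Bias would need lateness to differ by arm, and nothing in the protocol points to that. Discretion over late samples is also narrower than it seems, because excluding one would depart from the plain link between the visit and its sample.

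**Conclusion.** No change to the plan is called for. The contact-date phrase is a clerical slip: on the reading that Specific Aims, Approach and Table 1 support, no visit moves (shift 0 days). The missing window is a gap that an analyst fills sensibly by using the sample from the week 6 visit. Recording days from randomization to sample, and tabulating them by arm, is ordinary reporting and would show whether lateness was common or uneven.

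For a visit 7 days late, at most 7 of 49 days (14%) lie beyond study supply, and none do on the visit-by-visit account. The stated 200 completers and 80% power are unaffected.

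This rests on three assumptions: that collection dates are recorded, that week 6 is scheduled from the Baseline/Randomization visit, and that lateness does not differ materially by arm. The protocol gives no late-visit rate with which to test the last of these.

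The supply statements (next appointment plus 7 days, up to the week 6 visit, six weeks in total) contradict one another and must be reconciled by the sponsor. Which is right is not a statistical question, and the primary analysis is the same under any of them.
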